Calibration Phase I. The calibration phase of this study is designed to gather data to assist in developing an equation to account for the lag in TAC readings and transform these readings into an approximation of alcohol breath readings. In this calibration phase subjects will be given a measured dose of alcohol to achieve a peak BAL level of 0.05 g/dL after a one hour drinking session. The volume of alcohol will be calculated using an online tool developed by UW-Madison (<http://dionysus.psych.wisc.edu/WebCMS/baccalc.htm>) based on a formula described by Watson [14]. The hour-long drinking session will be followed by a five hour observation period to ensure that subject reach peak TAC. Blood alcohol level will be measured simultaneously using the transdermal sensors and the breathalyzer for the duration of the drinking period and observation period. Breathalyzer readings will be taken every 15 minutes during the entire experiment and transdermal sensors will log data continuously. To ensure residual alcohol in subjects' mouths does not provide a false breath alcohol reading, subjects will rinse their mouth twice with water after consuming a saltine cracker prior to each breathalyzer given while the subject is consuming alcohol. Subjects will remain in the drinking lab for up to five hours to allow for measurement of the peak transdermal alcohol concentration. Given the length of observation, we estimate that subjects will fully metabolize the alcohol they received during the calibration session and they will have a BAL of 0.00 g/dL when the calibration session is over. In the event that a drinking session is halted or the subject has a very slow rate of metabolism, we require that subjects remain in the laboratory until their BAL, as measured by breathalyzer, reaches 0.04 g/dL or less. The drinking session will be video-recorded to provide a record of the exact timing of breathalyzer readings. If methodology or safety issues are uncovered during the Phase I of this study, the protocol may be amended to address these issues prior to completing Phase II.

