Validation Phase II. Data from Phase I of this study will be used to develop a model to account for the lag in transdermal sensor readings relative to breathalyzer readings. Once all subjects have completed Phase I and the calibration model is complete, subjects will return to the laboratory to complete Phase II of the study. Given the expected time lag between Phase I and Phase II, eligibility will be re-assessed prior to the Phase II drinking session to ensure subject safety (see appendix A for schedule of events). If the subject remains eligible for Phase II of the study, the Phase II validation drinking session will be scheduled within 14 days of re-assessing eligibility. During the validation drinking session subjects will be given a measured dose of alcohol to achieve a peak BAL level of 0.05 g/dL after a one hour drinking session. The drinking period will be followed by a three-hour observation period. Blood alcohol level will be measured simultaneously using the transdermal sensors and the breathalyzer for the duration of the drinking period and observation period. Breathalyzer readings will be taken every 15 minutes during the entire experiment and transdermal sensors will log data continuously. To ensure residual alcohol in subjects' mouths does not provide a false breath alcohol reading, subjects will rinse their mouth twice with water after consuming a saltine cracker prior to each

Calibration Study of a Wearable Noninvasive Blood Alcohol Monitor

Final V1.8 4.24.19

breathalyzer given during the drinking period. Subjects will remain in the laboratory until their BAL, as measured by breathalyzer, reaches 0.04 g/dL or less.

Subjects: Subjects will be recruited through radio advertisements, newspaper advertisements, study flyers, social media, and internet postings. Interested subjects will be screened by telephone to determine initial eligibility prior to the baseline assessment.

6 Potential Risks and Benefits

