6.1 Risks

Physical discomforts:

The drawing of blood may cause pain, bruising, lightheadedness, and on rare occasions, infection. Subjects may briefly feel the prick of the needle when it is inserted. Subjects may feel dizzy or faint when blood is drawn. Trained phlebotomists will be used to minimize these risks.

ECGs may cause discomfort and/or irritation of the skin (redness and itching) from the adhesive electrodes. Hair on the subjects' chest may need to be removed in order to obtain the best electrical contact between the adhesive electrodes and subjects' skin. Trained staff will be used to minimize these risks.

Risk to recovery efforts

Treatment-seeking drinkers will be excluded from this study to minimize the risk that drinking in the laboratory could worsen outcomes for a subject trying to reduce or abstain from alcohol. All subjects will undergo a medical screening and we will exclude subjects who have a medical or mental condition for which alcohol exposure in this study would be contraindicated. All subjects will receive the NIAAA self-help guide *Rethinking Drinking* at the end of study participation [15].

Risk of overconsumption

To minimize the risk of subjects reaching a level of intoxication that is uncomfortable to them, we will remind subjects that they may discontinue study participation at any time. Subjects who qualify for this study will have experience consuming alcohol at an amount similar to the dose chosen for this study. Subjects will be monitored during the course of the study. Medical staff will evaluate subjects and may make a determination to halt study participation if the subject becomes too behaviorally impaired or if there are emergent safety issues. During the descending BAL period, subjects will have access to a comfortable space with entertainment (streaming media), snacks, non-alcoholic beverages, and a nearby bathroom.

Subject release:

- Subjects who have a BAL greater than .04 g/dl or who appear to be too behaviorally impaired to leave our research center will be asked to remain in the clinic until their

Calibration Study of a Wearable Noninvasive Blood Alcohol Monitor

Final V1.8 4.24.19

intoxication is reduced to a level that it is safe to discharge them from the research laboratory.

- Subjects will not be released within 60 minutes of their last drink consumed to ensure that peak BAC has been reached prior to discharge.

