Consenting subjects will undergo a general medical screen, including medical history physical examination. Drinking will be assessed using the TLFB [16], alcohol withdrawal using the Clinical Institute Withdrawal Assessment [17], and suicidality using the Columbia-Suicide Severity Rating Scale (C-SSRS) [18]. Exclusionary mental health conditions will be assessed using the MINI Neuropsychiatric Interview for DSM-5 [19]. Subjects will undergo urine toxicology and a urine pregnancy test for women of child bearing age. The baseline assessment may be completed in one or two visits.

Phase I BAL Calibration session:

Subjects will return to the laboratory within 14 days after completion of the baseline assessment to complete the Phase I BAL calibration session. For safety reasons, subjects will be asked to arrange transportation plans for this study visit. The alcohol lab visit is divided into four phases: 1) Screening, 2) Zero BAL observation, 3) Alcohol Administration, and 4) Observation.

1) *Screening.* Eligibility to continue in the study will be confirmed in a brief screening session. Subjects will undergo vital signs, alcohol breath test, urine drug screening, assessment of concomitant medications, assessment of alcohol withdrawal, urine pregnancy testing (for women), adverse event assessment, suicidality screening, and assessment of drinking since the

Calibration Study of a Wearable Noninvasive Blood Alcohol Monitor

Final V1.8 4.24.19

baseline. Blood alcohol level must be 0.000 to continue with the study procedures. Subjects will be excluded if urine toxicology results positive for cocaine, opioids, amphetamines, buprenorphine, methadone, or methamphetamines. Subjects will also be excluded if any concomitant medications that present safety issues for drinking have been started since the baseline assessment. Subjects will be excluded if the CIWA ≥ 10 or if the C-SSRS indicates any current suicidal ideation or behavior.

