If a subject completes Phase I and is unable to complete Phase II for any reason, replacement subjects will be recruited to complete Phase I and II consecutively. It is estimated that 36 subjects will be consented to yield 12 subjects that will complete Phase I and 9 subjects that will complete Phase II. Based on past experience with subject attrition, it is estimated that 33% of the Phase I subjects will be replaced at the time of phase II. Given the sample size requirements for this study are 9 subjects to complete both trials, the total sample size is estimated to be 12 subjects taking into account the possibility that three subjects will be lost to follow-up between trials one and two. If subjects are lost, when these subjects are replaced they will complete both the calibration session and validation session over the period of approximately 60 days.

Subject compensation

Subjects will be compensated up to \$340 for completion of all study activities. In addition to reimbursements for each study visit, subjects who complete all study visits will receive a completion bonus at the end of the study. If at any time subjects are discontinued from the study during a visit, subjects will be paid a portion of the payment based on time completed (e.g., 1

Calibration Study of a Wearable Noninvasive Blood Alcohol Monitor

Final V1.8 4.24.19

hour completed of two-hour visit = 1/2 of payment). Note there is an exclusion for payment due to UDS+ at the baseline.

Subjects will receive the following reimbursements:

Baseline assessment	\$40
Phase I BAL Calibration session	\$100
Phase II eligibility determination session	\$40
Phase II BAL validation session	\$100
Completion Bonus	\$60

10 Assessment of Safety and Data Safety Monitoring Plan (DSMP)

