10.3 Stopping Rules

There are no interim analyses planned that would allow for a determination of futility or overwhelming benefit. Study enrollment will be suspended under the following circumstances:

Calibration Study of a Wearable Noninvasive Blood Alcohol Monitor

Final V1.8 4.24.19

1. Serious Adverse Events. Study enrollment will be suspended in the event of a single serious adverse event that is determined to be unexpected and at least possibly related (i.e. it is an Unanticipated Problem). If suspended, study recruitment will not continue until a determination has been made about whether the known risks of participation have changed and the BU Medical Campus/Boston Medical Center IRB has made a finding that the risk/benefit ratio remains favorable given the possible newly identified risk.
2. Risk of intoxication. Subject recruitment will also be suspended if more than one subject of the first ten subjects enrolled is discontinued by the investigator due to intoxication during the alcohol self administration trial. Due to differences in alcohol tolerance, BAL is not a reliable measure of subjects potentially posing a safety risk. Medical staff will make a subjective determination of risk based on the subject's behavior. After 10 subjects have been enrolled, the trial will be suspended if there are more than 10% of subjects whose participation has been halted by the study team due to concerns about physical safety because of intoxication during the alcohol self-administration trial. If suspended for this reason, the study team will consider design changes to reduce the likelihood of this as a potential risk to study subjects. Recruitment would resume when the BU Medical Campus/Boston Medical Center IRB has made a determination that proposed changes to the study design have an acceptable risk/benefit ratio.

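### After a qualifying SAE, Section 10.3 item 1 suspends enrollment and recruitment but does not, as written, pause alcohol sessions in subjects already enrolled

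*Combined protocol and SAP*

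**What the plan says.** The lead-in to Section 10.3 (Stopping Rules) introduces its list as circumstances in which enrollment is suspended. Item 1 repeats that scope: "Study enrollment will be suspended in the event of a single serious adverse event", provided the event is unexpected and at least possibly related. The release condition is equally narrow: "If suspended, study recruitment will not continue until a determination has been made" about whether the known risks have changed and the IRB has found the risk/benefit ratio still favorable. Neither sentence mentions sessions in subjects who are already enrolled.

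Item 2 of the same section, on intoxication, is worded differently. For the first ten subjects it suspends recruitment. After ten it suspends the trial. Its release sentence then returns to recruitment resuming.

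The design is staged. Under Section 5, Validation Phase II begins "Once all subjects have completed Phase I and the calibration model is complete", and "the Phase II validation drinking session will be scheduled within 14 days of re-assessing eligibility". For Phase I, Section 9 says "Subjects will return to the laboratory within 14 days after completion of the baseline assessment". Section 9 plans for "12 subjects that will complete Phase I and 9 subjects that will complete Phase II", with replacements recruited for subjects who finish Phase I but cannot complete Phase II.

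**The concern.** Section 6.3 names alcohol consumption as the study's most significant risk, so the exposure that a safety hold needs to control is the drinking session. A hold on enrollment controls that exposure only while new subjects are still entering. By Phase II the original cohort is already in the study, and an enrollment hold reaches only replacements not yet recruited.

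Read literally, the rule therefore lets the remaining enrolled subjects be given alcohol after an unexpected, possibly related SAE and before the IRB has judged whether the risk/benefit ratio is still acceptable. Item 1 requires that judgment before new people are exposed. Subjects about to be dosed have the same claim to it.

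**Working it through.** The plan states no figure for this point, so there is none to reproduce. The check has two parts: a search for any other provision that would pause dosing, and a count of the sessions left outside the hold.

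**1. Does any other provision pause dosing in enrolled subjects?**

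- *Section 6.1, Risk of overconsumption.* "Medical staff will evaluate subjects and may make a determination to halt study participation if the subject becomes too behaviorally impaired"; the sentence goes on to add emergent safety issues as a second ground. This is discretionary and concerns the subject under evaluation. It does not require a pause for others.
- *Section 5, Calibration Phase I.* If problems come to light in Phase I, "the protocol may be amended to address these issues prior to completing Phase II". This is permissive and does not cover an SAE that occurs in Phase II.
- *Sections 5 and 9, eligibility checks.* These are made subject by subject and do not consider an SAE in someone else.
- *Section 10.3 item 2.* It refers to suspending the trial, but only for intoxication.
- *Section 10.4.* An Unanticipated Problem goes to the IRB within 2 days if fatal or life-threatening and within 7 days otherwise. No hold on sessions is stated for that interval.

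None of these is an automatic, study-wide pause after an SAE.

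**2. How many sessions fall outside the hold?**

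Inputs, from Section 9: 12 subjects complete Phase I and 9 complete Phase II.

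*SAE in Phase II session k of n.* Sessions remaining = n − k.

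| n | k = 1 | k = n | Mean if every k is equally likely (assumption) |
|---|---|---|---|
| 9 (planned completers) | 9 − 1 = 8 | 0 | (8 + 7 + … + 0)/9 = 36/9 = 4 |
| 12 (all return) | 12 − 1 = 11 | 0 | (11 + 10 + … + 0)/12 = 66/12 = 5.5 |

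If r of the remaining sessions belong to replacements not yet recruited, those are held and n − k − r stay outside. Section 9 allows for three subjects lost between phases. With r = 3 as an illustration, 8 − 3 = 5.

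*SAE in Phase I session k of 12, cohort fully enrolled.* Phase I sessions remaining = 12 − k, which gives 2, 1 and 0 for k = 10, 11 and 12. If the cohort is not yet full, the sessions outside the hold are those of subjects already enrolled and awaiting Phase I. The plan does not give that number. In that case the enrollment hold also delays Phase II indirectly, since Phase II waits for all subjects to finish Phase I.

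The documents give no SAE rate, so no probability is attached to any of these counts.

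**The case against.** The strongest reply is that this is loose drafting. Under one heading, Stopping Rules, the authors move between enrollment, recruitment and the trial, and item 2 itself suspends the trial and then resumes recruitment. On that reading they meant a general halt, and the investigator or the IRB would impose one anyway. This may well be so, and a reader should not infer that the plan intends dosing to go on after an SAE. It does not make the rule adequate, because staff cannot tell from item 1 what has to stop, and a stopping rule exists so that the action does not rest on discretion.

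A second reply is that safeguards are plentiful. The target is 0.05 g/dL in regular drinkers used to similar amounts, a nurse is on site until discharge, eligibility is checked at every visit, and safety monitors' reports go to the IRB. This stands. It limits the seriousness of the gap but does not close it.

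Two stronger readings are tempting and are not supported.

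- A reader might add all 9 Phase II sessions to the exposure after a Phase I SAE. Section 10.2 estimates 9 months between the two sessions, and the IRB is told within 2 or 7 days. Phase II would therefore probably follow IRB review, although the review time is not stated.
- A reader might also infer that the 14-day windows force a session during the hold. They limit when a session may be scheduled and oblige no one to dose. A session can fall due before the IRB is told, but it can be rescheduled.

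Finally, the protocol does not define when a subject counts as enrolled, so the position of consented subjects awaiting Phase I is arguable. The Phase II gap does not depend on that.

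**Conclusion.** The point holds as a defect in the written rule. It does not show that subjects are unprotected. Item 1 suspends only enrollment and recruitment, and no other provision requires a dosing pause across enrolled subjects.

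The gap matters mainly in Phase II. An SAE in the first session there leaves 8 of the 9 planned completer sessions outside the hold. Eight is not a ceiling: it is 11 if all 12 subjects return, and it is lower if some sessions belong to replacements not yet recruited. In Phase I the near-term exposure is the remaining sessions of subjects already enrolled.

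These counts take the planned numbers at face value, allow one Phase II session per subject, and leave out any Phase I session still owed by a replacement already enrolled. The analysis of the primary outcome is not affected. I would class this as a cheap improvement.

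**What to change.** Reword Section 10.3 item 1 along these lines:

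> Enrollment and all further alcohol administration, in both phases and including subjects already enrolled, are suspended after a single SAE that is unexpected and at least possibly related; neither resumes until the IRB has made its finding. A subject whose 14-day window lapses during the hold repeats the eligibility assessment before dosing.

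The windows should not simply be extended by the length of the hold. Appendix A schedules AST and ALT only at baseline and at the Phase II eligibility visit, so an extension would allow dosing on out-of-date safety screening just after an SAE.

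The cost is about two sentences in a protocol amendment, with nothing added if the rule never fires. If it does fire, sessions are delayed, some may run past the 9-month participation period, and some subjects may need a repeat eligibility visit.

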10.4 Reporting Plans

The Principal Investigator at BMC/BU Medical Campus will report Unanticipated Problems, safety monitors' reports, and Adverse Events to the BMC/BU Medical Center IRB in accordance with IRB policies:

- Unanticipated Problems occurring at BMC/BU Medical Campus involving a fatal or life-threatening event will be reported to the IRB within 2 days of the investigator learning of the event.
- Unanticipated Problems occurring at BMC/BU Medical Campus not involving a fatal or life-threatening event will be reported to the IRB within 7 days of the investigator learning of the event.
- Reports from safety monitors with recommended changes will be reported to the IRB within 7 days of the investigator receiving the report.
- Adverse Events (including Serious Adverse Events) will be reported in summary at the time of continuing review, along with a statement that the pattern of adverse events, in total, does not suggest that the research places subjects or others at a greater risk of harm than was previously known.
- Reports from safety monitors with no recommended changes will be reported to the IRB at the time of continuing review.

11 Data Handling and Record Keeping

11.1 Confidentiality

All staff will be fully trained in the procedures for protection confidential health information. To maintain subject confidentiality, study data will be coded on CRFs that are identified by a subject

Calibration Study of a Wearable Noninvasive Blood Alcohol Monitor

Final V1.8 4.24.19

number only. Source records with identifying information and CRFs will be stored in double-locked space with access only by authorized staff. Data stored in the REDcap system will have strong protections including file encryption and password access. Subject information will not be released without written permission. Upon approval of the study by an IRB, an application will be filed with NIAAA for a Certificate of Confidentiality.

11.2 Source Documents

Source documents in this study include:

Laboratory test results

Photocopies of the urine drug screening test result

ECG tracings

Subject locator form

Subject contact form

Data generated by the methods described in the protocol will be recorded in the subjects' source binder. Data may be transcribed legibly on CRFs for each subject or directly inputted into an electronic system or any combination thereof.

11.3 Case Report Forms

The study case report form (CRF) will be the primary data collection instrument for the study. All data requested on the CRF will be recorded. All missing data will be explained. If a space on the CRF is left blank because the procedure was not done or the question was not asked, a written explanation will be included to detail why the data was not recorded. If the item is not applicable to the individual case, a notation will be made. All entries will be printed legibly in black ink. If any entry error has been made, to correct such an error, a single straight line will be drawn through the incorrect entry and the correct data will be entered closely to the original data. All such changes will be initialed and dated. There will be no erasures or white-out on CRFs. For clarification of illegible or uncertain entries, the clarification will be printed near the item, then initialed and dated. Electronic CRFs in the REDcap system will include an audit trail.

The CRFs that will be used in this study are:

Demographics

Concomitant Medications

Adverse Events

Birth Control Assessment

Urine Drug Screening

Vital Signs

Blood Alcohol Level

Time-line Follow-back

Pregnancy test

Birth control assessment

Medical History

Physical Examination

Calibration Study of a Wearable Noninvasive Blood Alcohol Monitor

Final V1.8 4.24.19

MINI diagnoses summary

Medication Compliance log

Eligibility

ECG

C-SSRS

CIWA-AR

